Appendix 4. Patient Global Impression Severity-Impact on Daily Activities

Please rate the severity of the impact on daily activities due to the treatment administration during the past 4 weeks?

1. -“not present”.
2. -“very mild”.
3. -“mild”.
4. -“moderate”.
5. -“moderately severe”.
6. -“severe”.
7. -“extremely severe”.

Appendix 5. Schedule of Dyad Clinical Outcomes Assessments and Patient Global Impression Severity-Impact on Daily Activities Administration to Each Sub-group

Timepoint	Questionnaire	Subject only, aged 8-17 years	Subject/Caregiver Dyad	Caregiver only
Baseline	The Injection Pen Assessment Questionnaire (v2.0) Pen Ease of Use SECTION I The Injection Pen Assessment Questionnaire (v2.0) Ease of Injection Schedule SECTION I Patient Life Interference SECTION I Satisfaction & Willingness to Continue SECTION I Missed Injections (DAILY ADMINISTRATION) SECTION Patient Injection Signs & Symptoms (Ages 8 – 17 years) SECTION I	X	X X X X X	
Baseline	PGIS-IDA		X	
Baseline	Caregiver Assessment of Signs (Caregiver report for children aged below 8 years SECTION I) Caregiver Life Interference SECTION I			X X
Week 12 and week 24	The Injection Pen Assessment Questionnaire (v2.0) Pen Ease of Use SECTION I The Injection Pen Assessment Questionnaire (v2.0) Ease of Injection Schedule SECTION I Patient Life Interference SECTION I Satisfaction & Willingness to Continue SECTION I Missed Injections (DAILY ADMINISTRATION) SECTION I Missed Injections (WEEKLY ADMINISTRATION) SECTION I Patient Injection Signs & Symptoms (Ages 8 – 17 years) SECTION I	X	X X X X X	

Timepoint	Questionnaire	Subject only, aged 8-17 years	Subject/Caregiver Dyad	Caregiver only
Week 12 and week 24	PGIS-IDA		X	
Week 12 and week 24	Caregiver Assessment of Signs (Caregiver report for children aged below 8 years SECTION I) Caregiver Life Interference SECTION I			X X
Week 24 only	The Injection Pen Assessment Questionnaire (v2.0) SECTION II Patient Life Interference SECTION II Satisfaction & Willingness to Continue SECTION II Patient Intention to Comply with Treatment SECTION II		X X X X	
Week 24 only	Caregiver Life Interference SECTION II			X

**1. VERSION HISTORY**

Table 1. Summary of Changes			
Version/ Date	Associated Protocol Amendment	Rationale	Specific Changes
1 28 Feb 2019	Amendment 3 13 Nov 2018	N/A	N/A
2 15 Jul 2020	Amendment 5 26 Aug 2019	Clarification or completion of prior version	
Sections 2.2, 3.4, & 5.2.2. Region and type of injection device are no longer used as stratification variables.
 
Sections 3.3 & 6.3. Subject compliance was added as other endpoint.
 
Sections 3.5.1, 6.6, & 6.6.1. 3-tier approach for summarizing AE data was removed.
 
Section 4. ITT population was removed, Evaluable population was renamed to FAS, PPS was defined.
 
Section 5. ANCOVA model was removed.
 
CCI [REDACTED]
 
Sections 5.2.1, 5.2.3, & 8. Use of and reference to Gart (1969) was removed. CIs for proportions will use the Wilson score method.
 
Section 5.2.2. Analysis of continuous secondary endpoints will be performed using a linear mixed effects model.
 
Sections 5.3 & 6.1.1.2. Primary endpoint will now be performed on the FAS (completers restriction was removed) and sensitivity analysis on the PPS (completers); BOCF approach was removed.

			
Section 6.4. Burdened vs. not burdened was defined. Duplicated subset analysis was removed.
 
Section 6.5.2. Disposition events summary will now be presented by disposition phase.
 
Appendix 1.1. Visit windows for reporting were redefined.
 
Section 6.6.2. Some laboratory data summaries were removed.
 
Section 6.6.3. Vital signs summaries were removed.
 
Other typographical or administrative edits to improve readability and consistency.

3 01 Sep 2020	Amendment 5 26 Aug 2019	Better alignment with regulatory feedback and emerging guidance	
CCI [REDACTED]
 
Section 6.1.1.2. Two new sensitivity analyses were added.

**2. INTRODUCTION**

Note: In this document any text taken directly from the protocol is *italicised*, with exceptions noted where they appear.

*The majority of currently available hGH products require daily or every other day subcutaneous (SC) or intramuscular (IM) injections to maintain hGH blood levels within the effective therapeutic window. The burden of daily administration and its concomitant side effects (eg, injection site discomfort, transient edema and arthralgia) can cause a reduction in compliance and can limit the therapeutic utility of existing formulations.*

[figure not shown]
*Somatrogon is a long-acting r-hGH for SC administration. It consists of hGH fused to three copies of the C-terminal peptide (CTP) of the beta chain of human chorionic gonadotropin hCG; one copy at the N-terminus and two copies (in tandem) at the C-terminus.*

*Somatrogon is currently being developed for use as a long-term treatment in children with GHD. Five studies have been completed with somatrogon; two Phase 1 studies in healthy adult volunteers, two Phase 2 studies, in children and adults with GHD, and a Phase 3 study in adults with GHD. Results of the Phase 2 Study in children demonstrated pharmacokinetic (PK) and pharmacodynamic (PD) profiles compatible with once weekly administration. The*

estimated half-life ( $t_{1/2}$ ) of somatrogon was 22.4 hours in the 13 children receiving 0.66 mg/kg/week, compared with the  $t_{1/2}$  of r-hGH of 3.5 hours in the 11 children studied. IGF-1 serum levels for children receiving 0.46 mg/kg/week and 0.66 mg/kg/week remained above those of the children treated with r-hGH throughout the study. Clinical safety and efficacy was comparable to Genotropin® given once daily with no serious safety events.

The purpose of this study is to evaluate whether there is a benefit, defined as superior adherence and acceptance, of a once weekly injection schedule to support the benefit/risk profile of somatrogon. Figure 1 presents a conceptual model of the variables (precursors/predictors) hypothesized to be associated with adherence and treatment outcomes in GHD. While it is not possible at this time to evaluate adherence in a clinical trial, it is possible to instead evaluate some of these precursor variables.

**Figure 1. Hypothesized Conceptual Model of the Variables Associated with Adherence and Outcomes in GHD**

IPAQ: Injection Pen Assessment Questionnaire; HRQoL: health related quality of life

One component in this hypothesized model is treatment burden. Treatment burden relates to distress caused by treatment-associated demands (eg, visits to the doctor, medical tests, medication management, changes in lifestyle) which can have wide-ranging impact on patients' lives, and their caregivers. The burden associated with a treatment schedule may be one important consideration for adherence. The focus of the current study is to assess concepts (eg, device ease of use, side effects of treatment [eg, injection signs and symptoms], and life interference) that comprise key aspects of treatment burden in GHD. Specifically,

*this study tests the hypothesis that, for children with GHD, a once weekly treatment schedule (once weekly somatrogen) has a treatment burden that is less than a daily treatment schedule (Genotropin®).*

*A Dyad Clinical Outcomes Assessment (DCOA) questionnaire will be used to measure the variables as the growth hormone injection is often a shared experience between patient and caregiver. The DCOA questionnaire has recently been developed, and the development process complies with patient reported outcome (PRO) tool development as recommended by the Food and Drug Administration (FDA) and European Medicines Agency (EMA). The cognitive debriefing process via patient interviews resulted in the final content-valid version of the tools (ie, the relevant aspects of treatment burden etc were evaluated by the patient, and their understanding of the questions was also confirmed). The second key step was to conduct the Field Study in which the final tools were employed in patients who use daily growth hormone injections to determine the psychometric properties. The results demonstrated that the DCOA questionnaire performs well in this patient group; it is valid and reliable and is fit for purpose.*

This statistical analysis plan (SAP) provides the detailed methodology for summary and statistical analyses of the data collected in Study C0311002. This document may modify the plans outlined in the protocol; however, any major modifications of the primary endpoint definition or its analysis will also be reflected in a protocol amendment.

## **2.1. Study Objectives**

### Primary:

*To evaluate the treatment burden of a weekly somatrogen injection schedule and a daily Genotropin® injection schedule.*

### Secondary:

*To evaluate the following aspects of the treatment experience as determined by subject and caregiver self-assessments (dyadic approach) of weekly somatrogen therapy and daily Genotropin® therapy:*

- *Life interference;*
- *Caregiver life interference;*
- *Family life interference;*
- *Benefit, satisfaction, willingness to continue;*
- *Intention to comply;*
- *Injection pen ease of use;*

- *Convenience of injection schedule;*
- *Ease of the injection schedule;*
- *Preferred injection schedule;*
- *Choice of injection pen;*
- *Injection signs and symptoms (pain, bruising, stinging);*
- *Caregiver report of signs (bleeding, bruising);*
- *Missed injections.*

*To use a Patient Global Impression Severity-Impact on Daily Activities (PGIS-IDA) at baseline and at the end of each period (Week 12 and Week 24) to support the interpretation of scores from the Dyad Clinical Outcome Assessment (DCOA) 1 and DCOA 2 Questionnaires.*

CCI

#### Safety:

*To describe the safety and tolerability of somatrogon.*

[figure not shown]
### **2.2. Study Design**

*The study is a randomized, open-label, multi-center, 2-period crossover in children 3 to <18 years of age with GHD. The planned study duration is 24 weeks with a screening period of up to 30 days and a follow-up phone call four weeks after the last clinic visit. Approximately 90 children with GHD who have been stable on treatment with daily Genotropin® for a minimum of 3 months will be enrolled. Subjects will be randomized to one of two sequences, either 12 weeks of continued treatment with daily Genotropin® followed by 12 weeks of treatment with weekly somatrogon, or 12 weeks of treatment with weekly somatrogon followed by 12 weeks of treatment with daily Genotropin® (see [Figure 2](#) below). There will be no treatment wash-out period since these subjects must take growth hormone continually.*

*Subjects will have study visits at Baseline, Weeks 6, 12, 18, and 24. Subjects will also be followed up by phone 8-12 days after each treatment period begins (Week 1 and Week 13). Subjects and caregivers will complete the DCOA questionnaires at baseline and at the end of each 12 week treatment period (DCOA 1 at baseline and after Period I and Period II; DCOA 2 after Period II). Subjects and caregivers will also complete the PGIS-IDA at baseline and after Period I and Period II. Appendix 5 within the protocol describes which*

*sub-group (subject and/or caregiver) completes which part of the questionnaire and at which time point. All subjects/caregivers will receive a follow up phone call at week 28.*

**Figure 2. Study Design**

### 3. ENDPOINTS AND BASELINE VARIABLES: DEFINITIONS AND CONVENTIONS

In general, all the DCOA and PGIS-IDA assessments employed can be classified into one of six item types with one of the following types of response scales:

1. 11-point numeric rating scale with values 0 – 10: this scale is used for assessing pain, stinging, bruising, and bleeding;
2. 5-point Likert-type scale with values 1 – 5: this scale is used for assessing ease of use, ease of following injection schedule, life interference, and treatment satisfaction;
3. 7-point Likert-type scale with values 1 – 7: this scale is used for assessing convenience of following injection schedule and impact on daily activities;
4. Continuous scale with values 0 – 31 (open field): this scale is used for assessing the number of missed injections;

CCI [REDACTED]

[REDACTED]

[REDACTED]

[REDACTED]

[REDACTED]

[REDACTED]

[REDACTED]

CCI [REDACTED]

[REDACTED]

### 3.1. Primary Endpoint

There are eight variables to assess treatment burden and they are:

1. A measure of the severity of signs and symptoms of pain, stinging, bruising, and bleeding;
2. A multiple dimension assessment of handling characteristics of injection devices;
3. A measure of overall ease of use of the injection pen;
4. A measure of overall ease of use of the injection schedule;
5. A measure of overall convenience of the injection schedule;
6. A measure of life interference (daily activities/social activities/leisure/night away from home/travel);
7. A measure of how often changes are made to life routine; and
8. A measure of how often the growth hormone injections cause bother, respectively.

CCI [REDACTED]

*Treatment burden assessed as the difference in mean Overall Life Interference total scores between the weekly injection schedule and daily injection schedule as assessed by the Patient*

*Life Interference Questionnaire (as part of DCOA 1) completed by the Subject/Caregiver Dyad at baseline and after each treatment schedule experience.*

### **3.2. Secondary Endpoints**

#### **3.2.1. Treatment Experience Assessed using DCOA 1 Questionnaire**

*Treatment experience assessed as the difference in mean scores between the weekly injection schedule experience and daily injection schedule experience in each of the following variables within DCOA 1 questionnaires completed at baseline and after subjects have experienced both treatment schedules:*

- *Pen ease of use (5 questions, 5-point scale each);*
- *Ease of the injection schedule (1 question, 5-point scale);*
- *Convenience of the injection schedule (1 question, 7-point scale);*
- *Satisfaction with overall treatment experience (1 question, 5-point scale);*
- *Willingness to continue injection schedule (1 question, 5-point scale);*
- *Injection signs and symptoms (from the patient aged 8 years and over) (4 questions, 0-10 scale each);*
- *Assessment of signs (from the caregiver for children aged <8 years) (2 questions, 0-10 scale each);*
- *Caregiver life interference, including family life interference (13 questions, 5-point scale each);*
- *Missed injections (1 question, # 0-31 for daily administration, # 0-5 for weekly administration).*

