5.4.2. Missed Doses

Subjects on somatrogon should administer their dose once weekly at approximately the same time on a regularly scheduled day of the week. If a subject on somatrogon misses a dose, they should administer that dose as soon as they remember, provided it is no more than 72 hours after their regularly scheduled dose. If the dose is more than 72 hours from their regularly scheduled day of the week, then the patient shall skip the dose for that week and resume dosing on their next regularly scheduled day of the following week. Note: Doses that are administered within 72 hours of their regularly scheduled day of the week will not be considered a missed dose.

Subjects on Genotropin[®] should administer their dose once daily at approximately the same time every day as they were at the time of screening. If a subject on Genotropin[®] misses a dose, they should administer that dose as soon as they remember, provided it is within 10 hours of their regularly scheduled dose. If more than 10 hours have passed the subject should resume administration of the study medication at the next scheduled time. Subjects should not double any doses to make up for a missed dose.

Subjects will be trained that if an injection is started (ie, the injection device is placed on the skin with the needle inserted into the skin and the button is depressed) no further attempts at injection should be made for that scheduled dose even if there is uncertainty that the full dose was received.

Subjects will record dose administration in the subject diary; this is how compliance will be determined.

A question involving missed doses and reason for missing is part of DCOA1 but is not being used to determine compliance.

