### 5.1. Hypotheses and Decision Rules

For the primary endpoint analysis conducted after all subjects complete their 24 weeks of treatment (Visit 7), the hypothesis will be tested that overall mean Life Interference score (based on the 7 questions) is lower for weekly somatrogon compared to daily Genotropin.

CCI [REDACTED] Therefore, results of the primary endpoint hypothesis test, including the two-sided p-value, will be reported, but the p-value does not need to meet a specific threshold.

The sample size for the study was based on internal expert opinion with the following assumptions using a two-sided type-I error of 0.05:

CCI [REDACTED]

[REDACTED]

Under the above assumptions, a total of 75 subjects are needed at 90% power from a two-sided paired t-test for mean difference for the proposed study using Life Interference as the primary endpoint. CCI [REDACTED]

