### **5.2.2. Analyses for Continuous Endpoints**

A linear mixed effects model including sequence, period, and treatment as fixed effects and subject within sequence and within-subject error as random effects will be used for analyzing the primary endpoint and continuous secondary endpoints. This model will be used to obtain the estimate, CI, and p-value for the treatment effect and other effects of interest.

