#### **6.2.1. Treatment Experience Assessed using DCOA 1 Questionnaire**

Treatment experience assessed as the difference in mean scores between the weekly injection schedule experience and daily injection schedule experience in each of the following

variables within DCOA 1 questionnaire completed at baseline and after subjects have experienced each treatment schedule:

- Pen ease of use,
- Ease of the injection schedule,
- Convenience of the injection schedule,
- Satisfaction with overall treatment experience,
- Willingness to continue injection schedule,
- Injection signs and symptoms (from the patient aged 8 years and above),
- Assessment of signs (from the caregiver for children <8 years old),
- Caregiver life interference, including family life interference,
- Missed injections.

These variables will be analysed and summarized in the same way as the primary endpoint ([Section 6.1.1.1](#)).

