### 6.3. Other Endpoints

Number of subjects satisfying or not satisfying the compliance threshold of  $\geq 80\%$  adherence to injections will be presented by each treatment period (Week 12 and Week 24) and overall by treatment. Additionally, adherence will be summarized descriptively as a continuous variable, where adherence is defined as

$$\left(1 - \frac{\text{number of missed doses}}{\text{total number of doses subjects were supposed to take}}\right) \times 100.$$

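### On the readable text, missed injections are modelled as raw counts with no denominator, so equal non-zero miss rates produce a difference in favour of weekly dosing

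*SAP*

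**What the plan says.** SAP Section 3 classes the response as an open-field number from 0 to 31 and says that "this scale is used for assessing the number of missed injections". SAP 3.2.1 lists the item among nine DCOA 1 variables as "Missed injections (1 question, # 0-31 for daily administration, # 0-5 for weekly administration", under an endpoint defined as "Treatment experience assessed as the difference in mean scores between the weekly injection schedule experience and daily injection schedule experience". SAP 6.2.1 then says of all nine: "These variables will be analysed and summarized in the same way as the primary endpoint". The model, in SAP 5.2.2, is "A linear mixed effects model including sequence, period, and treatment as fixed effects", with subject within sequence and within-subject error as random effects. It has no offset or exposure term, and it yields an estimate, a confidence interval and a p-value.

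The only readable denominator is in SAP 6.3: "Additionally, adherence will be summarized descriptively as a continuous variable, where adherence is defined as" one minus missed doses over doses due, times 100. That is a separate endpoint in the other-endpoints section, with no model or test. Protocol 5.4.2 takes compliance from the diary and sets this item apart: "A question involving missed doses and reason for missing is part of DCOA1 but is not being used to determine compliance".

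Text after the list of response scales in SAP Section 3, most of SAP Appendix 1 (data derivation) and the item wording in Protocol Appendix 3 are redacted.

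**The concern.** A count of missed injections depends on two things: how often a scheduled injection is missed, and how many were scheduled. The schedules under comparison differ in the second by design. A difference in mean counts mixes the two, and for any common recall window the number scheduled pulls the contrast towards weekly.

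This matters because both documents state the study's purpose as showing better adherence and acceptance of weekly dosing. A significant difference in missed injections is likely to be read as evidence of adherence, although the dosing schedule alone can produce it. The plan fits a model to the measure that cannot separate the two, and only describes the one that can.

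**Working it through.** **Inputs.** The documents give no miss rate and no planned effect for this item, so there is no figure of the plan's own to reproduce here.

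- Item ranges: 0–31 daily, 0–5 weekly (SAP 3.2.1).
- Sample size: about 90 (Protocol 9.1). Two-sided 5% level.
- Recall window (assumed, because the item text is redacted): from 4 weeks, giving 28 daily and 4 weekly doses, to the item maxima of 31 and 5. The 4-week figure is the recall period of another DCOA 1 item quoted in SAP 6.4.
- Miss rates and between-subject variation: assumed.

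**Expected difference at equal miss rates.** With miss probability p, the expected count is doses × p. Weekly minus daily is therefore (4 − 28)p = −24p, or (5 − 31)p = −26p. The daily mean is 28/4 = 7.0 or 31/5 = 6.2 times the weekly mean. The sign does not depend on the window; the size does.

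**Chance of a significant result at equal miss rates.** The simulation used a 2×2 crossover with 45 subjects per sequence and a period-adjusted t-test. Misses were beta-binomial with intraclass correlation 0, 0.1 or 0.3, and each subject's tendency to miss was shared or independent across periods. Both windows were used, with 1,000–3,000 runs per setting.

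| Missed on both | 28 vs 4: daily, weekly, difference | 31 vs 5: daily, weekly, difference | p<0.05 for weekly |
|---|---|---|---|
| 0% | 0, 0, 0 | 0, 0, 0 | none |
| 1% | 0.28, 0.04, −0.24 | 0.31, 0.05, −0.26 | 15–99% |
| 2% | 0.56, 0.08, −0.48 | 0.62, 0.10, −0.52 | 55–100% |
| 5% | 1.40, 0.20, −1.20 | 1.55, 0.25, −1.30 | 98–100% |

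With 74 subjects the 5% row becomes 94–100%. A simpler simulation (paired t-test, 75 or 90 subjects, independent misses or a shared subject rate with correlation 0.1) gave 78–99% at 1%, at least 99% at 2% and about 100% at 5%. The wide range at 1% reflects the assumed heterogeneity.

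**When weekly is truly worse.** Daily is held at 5% missed.

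| Weekly missed | Difference, 28 vs 4 | Difference, 31 vs 5 | Raw count: p<0.05 for weekly | Percentage: p<0.05 for daily |
|---|---|---|---|---|
| 10% | 0.4 − 1.4 = −1.0 | 0.5 − 1.55 = −1.05 | 78–100% | 50–99% |
| 15% | 0.6 − 1.4 = −0.8 | 0.75 − 1.55 = −0.8 | 46–100% | 95–100% |
| 30% | 1.2 − 1.4 = −0.2 | 1.5 − 1.55 = −0.05 | 1–24% | not computed |

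Mean counts become equal only when weekly misses reach 0.05 × 28/4 = 35%, or 0.05 × 31/5 = 31%.

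**Percentage scale at equal rates.** The expected difference is 0. The linear model's two-sided type I error was 4.6–6.1% at 5% missed, 4.7–6.8% at 2% and 4–10.5% at 1%.

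**The case against.** - **Redaction.** A conversion to a rate could sit in the blacked-out scoring or derivation text. This stands as a limit: the point applies to the readable text only, and the sponsor must check first.
- **Already covered in SAP 6.3.** The adherence percentage is reported by period and by treatment, and the DCOA 1 item is not used for compliance. Both are true, but the 6.3 measure is only descriptive, and the item remains a listed secondary endpoint with a modelled contrast.
- **A different question.** The item sits under treatment experience, and fewer missed injections per month is a real difference in counts. On that reading the rejection rates above are not false positives for the stated endpoint. This is fair for a description. It does not support an inference about how reliably doses are taken, which is the natural reading given the study's stated purpose.
- **Assumed magnitudes.** The window, the miss rates and the heterogeneity are not in the documents. Entry requires prior compliance, so low rates are plausible, and at 1% missed the effect on significance ranges from modest to near-certain. This stands for the size, not for the sign.
- **Reach.** SAP 5.1 says even of the primary test that "the p-value does not need to meet a specific threshold", and no readable success criterion uses this item. This stands, and it limits the seriousness.

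**Conclusion.** The concern holds on the readable text. At any equal, non-zero miss rate the planned contrast favours weekly, by 24 to 26 times the miss rate under the assumed windows. At about 5% missed, a significant result for weekly is close to certain even with equal adherence. The contrast can also point the wrong way: with 5% missed on daily and 15% on weekly, it still favours weekly by 0.8 injections, while the percentage scale shows weekly worse by 10 points. If nobody misses an injection there is no distortion.

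The sign needs only a common recall window and no hidden rate conversion. The sizes rest on the assumed windows, miss rates and heterogeneity. The plan should be corrected, but the effect is confined to the interpretation of one secondary variable.

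**What to change.** First confirm whether the redacted scoring or derivation text already turns this count into a rate. If it does not, amend SAP 3.2.1 and 6.2.1 so that the analysed variable is missed injections divided by injections scheduled in the item's recall window, times 100. This is the scale behind SAP 6.3. Fit it in the same crossover model, or preferably in a binomial mixed model with scheduled injections as the denominator. Keep the raw counts as descriptive, by schedule.

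The cost is SAP wording and one derived variable; the denominator follows from the recall window and the dosing schedule, so no new data are needed. The drawback is a coarse weekly percentage, in steps of 20 to 25 points with 5 or 4 doses. The linear model's type I error also rises to about 10.5% in some settings at 1% missed, which is the reason for preferring the binomial model. That model was not simulated and may itself be fragile when misses are rare: at 1% missed, 90 × 4 = 360 weekly doses give only 3.6 expected events. A fallback for sparse data should be specified in advance.
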